Aim #1. Determine the immediate and retention effects of power training combined with interval treadmill training (PT³) on functional walking capacity in ambulatory children with CP.

We hypothesize that a combined impairment and task-specific approach, which targets muscle power deficits specifically, will have a significant effect on functional walking capacity as compared to an equivalent dosage of traditional impairment-based and task-specific approaches. In a randomized clinical trial, 48 ambulatory participants with CP (10 to 17yrs) will receive either PT³ or an equivalent dosage of traditional strength training combined with traditional treadmill training (comparison group) for 24 sessions, 3 times per week for 8 weeks. Outcomes will be collected at baseline and immediately post-treatment. Short and long-term retention effects will be assessed at 2 and 6 months post. Self-selected gait speed will be the primary outcome with secondary outcomes of fast gait speed, the 1-Minute Walk test and Timed-up-and-Go.

Aim #2. Quantify the effects of treatment on *in vivo* muscle architecture and muscle performance.

We hypothesize that lower extremity muscle power generation is impaired and is responsible for limitations in walking activity, and that PT³ will result in significant improvements in muscle power that will be explained partly by increases in cross-sectional area and fascicle length. Muscle architecture will be measured with ultrasound imaging, and muscle performance outcomes will be measured with isokinetic dynamometry.

Aim #3. To directly capture the effect of treatment on community-based walking activity and participation, we will use a novel combination of global position system (GPS) and accelerometry.

For this exploratory aim, we hypothesize that improved walking capacity from PT³ will enhance community-walking activity and participation captured in real-world settings. We will use coordinate data from GPS devices synchronized with StepWatch accelerometers to directly measure strides per day, stride rates, distance, duration, and location. This novel technology will allow us to better characterize walking activity outside of the clinic/laboratory setting and has far-reaching clinical implications.

Significance and Background

Gait impairments and deterioration in ambulatory children with Cerebral Palsy (CP)

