This is a multi-center RCT. We will enroll 48 participants (24 per site). Participants will be randomized to receive either PT3 or the comparison intervention. We will employ a randomized block design with two blocking factors, GMFCS level and study site. This will address any clinical heterogeneity of outcome measures by functional level and study site. Outcomes assessors will be blinded to group assignment. The study biostatistician, [name], will generate randomization sequences in accordance with the study design.

Recruitment

Participants will be recruited from the local hospitals and physical therapy clinics. Colleagues will be sent emails and/or letters describing the purpose of the study and criteria and asking them to share the study

information and my contact information with their patients. IRB-approved letters of support from colleagues, study flyer, and a provider approach template letter will be utilized for recruitment.

Identification of potential participants may also occur through the Louisiana Children's Medical Center electronic medical record (EMR) system known as EPIC in conjunction with Children's Hospital New Orleans (CHNOLA). A request from LSUHSC personnel will be sent to CHNOLA's Director of Research Operations using the previously mentioned inclusion criteria, desired PHI (i.e. first and last name, date of birth, address, etc.), and ICD-10 codes. The CHNOLA Director of Research Operations will create an IT Ticket and send it to EPIC to have a report generated with all requested data. After receiving PHI, LSUHSC personnel will perform a basic review of the participant's medical records to identify whether or not the participants meet basic eligibility requirements. Patients identified as a potential participant will be initially contacted by the CHNOLA Site PI (i.e. direct mail, EPIC messages, email, etc.), however all contact thereafter would be handled by the LSUHSC personnel. An approach mailing will include IRB-approved materials, including: approach letter, study flyer, return letter of interest and postage paid envelope to return letter of interest to study staff LSUHSC-NO. Approach email will include IRB-approved materials, including: approach letter, study flyer, and contact information of study staff at LSUHSC-NO.

Protocols and Timeline

Intervention Protocols:

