Power Calculations: The sample size calculations for Specific Aim 1 focus on assessing differences in changes from baseline to 8 weeks in mean outcome between the PT3 and control groups. Estimates of variability and clinically relevant effect sizes for Specific Aims 1 & 2 were obtained from preliminary data for the treatment effect estimates and from [name] et al. (2013) for the comparison group effect estimates. Assuming a statistical model for a replicated randomized complete block experiment with fixed treatment factor (PT3 vs comparison) and a 0.050 two-sided significance level, the null (primary) hypothesis of no difference in mean change from baseline to 8 weeks in self-selected gait speed between groups will have 90% power to detect a difference of 0.12 m/s given a common standard deviation of 0.167 m/s with a sample size of n=24 per group. A sample size of 24 in each group will also have 79% power to detect a difference of 0.137 m/s in fast gait speed, assuming a common standard deviation of 0.127 m/s. Specific Aim 2: A sample size of 24 in each group will have 99% power to detect a difference in mean peak power of 0.819 watts/kg with a common standard deviation of 0.485 watts/kg with a 0.050 two-sided significance level. A sample size of 24 in each group will have 90% power to detect a difference in mean fascicle length of 1.55 cm given a common standard deviation of 1.61 cm. Specific Aim 3: Average number of strides per day (over a 5 day period) were obtained from [name] et al. (2014) with the differences observed between GMFCS levels II and II used to approximate the expected differences between treatment groups. Assuming a common standard deviation of 1,580 average strides/day, a sample size of 24 will have 90% power to detect a difference in average strides/day between treatment groups as small as 1,510 strides/day. In the event that we experience dropout, the primary analysis of each aim will still have > 80% power to accommodate as high as a 25% dropout rate (n=19 per group).

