Data Analysis Plan: The primary analysis will compare differences in changes from baseline to 8 weeks post in mean response between the treatment and comparison group using a general linear model with blocking factors for intervention site and GMFCS levels as fixed factors. By employing a randomized block design, we can statistically account for any clinical heterogeneity of outcomes by study site and GMFCS levels should this occur. To gain insight into both short and long-term retention of treatment effects, response profiles over the 4 time points will be compared using a linear mixed effects model with sites and GMFCS level as blocking factors, treatment group and time as fixed effects factors, and subjects as a random factor. These models will be used for analysis of the primary and secondary response variables of Specific Aims 1 and 2. The outcomes of Specific Aim 3 will use similar analysis models but will include an additional factor to allow comparison between home and community walking activity as a separate analysis. To assess the potential impact of gender on study outcomes, gender will be included in each of the models as a fixed effect. If significant gender effects are observed, we will report both adjusted and unadjusted estimates of treatment effects to more fully reveal the role of gender. Type I error rate will be set at 0.05. The primary dataset for analysis is the intent-to-treat dataset consisting of all patients randomized to intervention. The Statistical Analysis System (SAS®), V9.4 will be used for statistical analysis using GLM and MIXED procedures.

Data Management and Fidelity: REDCap™ will be used for data management. REDCap™ is a secure application designed for building and managing databases to allow electronic data collection from multi-site studies and allows instantaneous access to data. [name] will provide oversight to extensive quality control checks incorporated into the data entry system, such as real-time validation rules (with automated data type and range checks) at the time of data entry, and tracking of critical study events, such as assessment and

intervention visits requiring physical oversight as described previously. Data management principles will be implemented to ensure the integrity, security, and confidentiality of all study-related data.

Project Timeline

Task:	Year 1			Year 2			Year 3			Year 4			Year 5		
Train Intervention/Assessment staff	X	X													
Seattle site visit by PI	X	X		X			X				X				

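### A 25% dropout from 24 per group leaves 18, not the stated 19, so the power claim after dropout is tied to the wrong sample size

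*Combined protocol and SAP*

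**What the plan says.** The Power Calculations section sizes the trial "with a sample size of n=24 per group". This agrees with Study Design and Randomization: "We will enroll 48 participants (24 per site"), that is, 48 in two arms. The last sentence of Power Calculations then says that "the primary analysis of each aim will still have > 80% power to accommodate as high as a 25% dropout rate (n=19 per group").

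The model behind the calculations is described as follows: "Assuming a statistical model for a replicated randomized complete block experiment with fixed treatment factor (PT3 vs comparison"). The design section names the blocks: "We will employ a randomized block design with two blocking factors, GMFCS level and study site". The Data Analysis Plan carries them into the primary analysis, "using a general linear model with blocking factors for intervention site and GMFCS levels as fixed factors". The plan does not say whether the printed standard deviations are before or after removing block variation.

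No other section gives a different starting number, dropout rate or rounding rule that would turn 25% of 24 into a loss of five.

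**The concern.** The sentence is the plan's only statement of how much loss to follow-up the trial can absorb. A reader will take from it that losing a quarter of each arm, 6 of 24, still leaves more than 80% power in every aim. The number in brackets covers a loss of five.

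One child per group would not matter if power were comfortably above the target. For two of the outcomes sized in this section it is not. Their power at 19 per group is only about two points above 80%, and one more loss per group costs about two points. So the mismatch decides whether the claim has any margin at the dropout rate it names.

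**Working it through.** **Inputs, all from Power Calculations.** 24 per group; two-sided α = 0.05; 25% dropout; 19 per group remaining. Difference and SD: fascicle length 1.55 and 1.61 cm; peak power 0.819 and 0.485 watts/kg; strides/day 1,510 and 1,580.

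**Step 1: the dropout arithmetic.**
- Remaining after 25%: 24 × (1 − 0.25) = 18 per group, exactly; 48 × 0.75 = 36 in total.
- Dropout implied by 19: 1 − 19/24 = 5/24 = 20.8% (38 in total).
- Enrolment needed to keep 19 after a true 25% loss: 19 / 0.75 = 25.3, so 26 per group.

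A possible origin, by inference only, is that 19 × 1.25 = 23.75, which rounds up to 24. That is a 25% inflation factor labelled as a dropout rate. The point does not depend on it.

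**Step 2: reproduce the plan's power at 24 per group.** Two-sample t-test without blocking: noncentrality (Δ/SD) × √(n/2), with 2n − 2 degrees of freedom. For fascicle length, (1.55/1.61) × √12 = 0.963 × 3.464 = 3.34 on 46 df, which gives 90.4%.

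| Outcome | Stated, n=24 | Recomputed, n=24 | n=19 | n=18 |
|---|---|---|---|---|
| Fascicle length (Aim 2) | 90% | 90.4% | 82.3% | 80.1% |
| Peak power (Aim 2) | 99% | 99.99% | 99.9% | 99.8% |
| Strides/day (Aim 3) | 90% | 90.0% | 81.8% | 79.5% |

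The stated figures at 24 are recovered, so the same test is a fair yardstick for 19 and 18.

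**Step 3: how far the result depends on method.**
- Normal approximation at n=18: fascicle length 82.3%, strides/day 81.8%. Both stay above 80%.
- Block model at n=18. Assumptions: printed SDs are before blocking; 3 df are removed (1 for site, 2 for GMFCS level); blocks explain 0% to 10% of variance, a range the documents do not give. Fascicle length runs from 79.9% to 83.9% and strides/day from 79.3% to 83.3%. Power reaches 80% once blocks explain about 0.3% and 1.7% of variance respectively.
- The Data Analysis Plan also puts gender in each model. With 4 df removed, those thresholds become about 0.5% and 1.9%, which changes nothing of substance.

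**Step 4: Aim 1, kept apart.** The plan says the primary outcome "will have 90% power to detect a difference of 0.12 m/s given a common standard deviation of 0.167 m/s". With those inputs the t-test gives 68.3% at n=24, 57.8% at n=19 and 55.4% at n=18. The claim of more than 80% therefore fails for Aim 1 before any dropout, whichever n is used. If the SD were 0.127 m/s, the figure printed for fast gait speed, power would be 89.3%, 80.9% and 78.6%. The documents do not confirm that reading.

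**The case against.** The strongest reply is that only a label is wrong. At the n actually printed, power does exceed 80% for every Aim 2 and Aim 3 outcome, and by the t-test 19 is the smallest group size that does so for strides/day. That suggests 19 was the calculated quantity and 25% the slip. The consequence is also small:
- Peak power is untouched, and the plan never names fascicle length as the primary outcome of Aim 2.
- Fascicle length is still 80.1% at 18.
- Strides/day falls short by only half a point, in an aim the plan itself calls exploratory ("For this exploratory aim, we hypothesize that improved walking capacity from" PT³ community walking will improve).
- A normal approximation or a small gain from blocking removes even that shortfall.

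Most of this stands, and it limits the weight of the point: a power failure is not shown. It does not rescue the sentence. The claim is made for each aim and at 25%, and under any model a quarter of 24 is six. A tolerance of one or two participants is reasonable when formulas or rounding rules differ, but this multiplication has a whole-number answer.

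**Conclusion.** The point holds. The stated 25% and the stated 19 per group cannot both be right: 25% is 18 per group, and 19 per group is 20.8%. This needs no modelling assumption.

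The effect on power is minor. The t-test figures rest on the printed differences and SDs and on no gain from blocking. On that basis fascicle length has essentially no margin at a true 25% loss and strides/day sits marginally below 80%. Whether 80% is met depends on how the SDs were obtained, which the plan does not state. Aim 1 is excluded from this conclusion because its printed SD already contradicts its stated power at full enrolment.

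**What to change.** Change the last sentence of Power Calculations in one of two ways.

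1. Keep the group size and correct the rate: about 20% dropout (n=19 per group; 5 of 24, 20.8%). This is the simpler repair, and for Aims 2 and 3 the claim of more than 80% then stands on the printed inputs.
2. Keep 25%, write n=18 per group, and replace the blanket claim of more than 80% with the power recomputed for each aim under the planned block model, saying whether the SDs are before or after blocking.

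In either version, restate the Aim 1 figure once its gait-speed SD has been reconciled, and do not claim more than 80% for Aim 1 if 0.167 m/s stands.

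The cost is one sentence. Enrolment of 48, the design and the analysis do not change. The only drawback is a less favourable statement: a tolerance of about 20% rather than 25%, or power close to 80% for fascicle length and strides/day at 25% dropout.

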Fidelity of Interventions: Intervention fidelity across sites will be addressed by in-person training of all intervention therapists by [name] employing an intervention visit procedural checklist of visit tasks. Intervention therapists must reach 100% performance and completion prior to study initiation. Training videos and manuals will be provided for reference. Interventionists will complete checklist for every study visit with physical monitoring of intervention visits by the site PI at weeks 1, 4 and 7 for each participant with real-time feedback provided. If performance falls <95%, the interventionist will repeat training.

Testing / Assessment Protocols

Procedures: Outcomes will be assessed pre and post intervention to determine immediate effects of treatment; at 2 months post for short-term retention; and 6 months post for long-term retention (Figure 4). The goal will be to perform the baseline assessment within 1 week prior to the start of the intervention and within 1 week of completing the intervention for the post assessment but must always occur a minimum of 48 hours before or after a training session for baseline and post-assessment, respectively. However, a 2-week window will be allowed for all assessment timepoints.

[figure not shown]

Figure 4. Experimental design for 8-week interventions and timeline for assessment. TT = treadmill training

Outcome Measures: Assessors will be blinded to group assignment.

- 1) **Clinical Assessment:** Anthropometric measurements (height, weight, leg length, lower leg length, thigh length) will be collected. Knee and ankle range-of-motion will be measured. The child will be classified according to the Gross Motor Function Classification System (GMFCS), levels I, II, or II.

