- 2) **Walking Capacity:** Self-selected and fast walking speeds will be calculated from the 10-m Walk Test as the average of three trials each (33). The time that it takes to walk a distance of 10 meters is recorded. Walking capacity will also be measured with the 1-minute walk test (1MWT), in which the distance the child can walk as fast as possible in one minute is calculated (34). For the Timed up and Go (TUG) test, the child is asked to stand up from a standard chair and walk a distance of approximately 10 feet (measure as 3 meters), turn around and walk back to the chair and sit down again (46). All measures have been widely used in this population in clinical settings and shown to be reliable measures (33-34, 46). Participants will also be videotaped while walking on the treadmill from the front/back view and a side view. The walking videos will be analyzed for quality of gait using the Edinburgh Visual Gait Score.

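### The primary change-score model leaves out the measured baseline value of the outcome; adding it is a cheap, low-severity gain in precision

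*Combined protocol and SAP*

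**What the plan says.** The Data Analysis Plan defines the primary analysis in these terms: "The primary analysis will compare differences in changes from baseline to 8 weeks post in mean response", between the two arms, by a "general linear model with blocking factors for intervention site and GMFCS levels as fixed factors". It then states that "gender will be included in each of the models as a fixed effect". The fixed terms are therefore treatment, site, GMFCS level and gender.

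A second model serves the retention question: "response profiles over the 4 time points will be compared using a linear mixed effects model". Of the two models together the plan says "These models will be used for analysis of the primary and secondary response variables of Specific Aims 1 and 2".

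The baseline value is available. Specific Aims states that "Outcomes will be collected at baseline and immediately post-treatment", and Testing / Assessment Protocols that "Outcomes will be assessed pre and post intervention to determine immediate effects of treatment". For the primary outcome, "Self-selected and fast walking speeds will be calculated from the 10-m Walk Test as the average of three trials each". No section enters that baseline value in the primary model.

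**The concern.** Analysing change without a baseline term assumes that each extra 1 m/s at baseline carries through to exactly 1 m/s at 8 weeks. If the true slope within site and GMFCS level is below 1, as happens with measurement noise or regression to the mean, part of the variance of change is predictable from baseline and could be removed. GMFCS level is only a three-category proxy for a continuous gait speed, so blocking on it does not do this job.

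Only precision is at stake. A chance baseline gap between arms does leave an error in the change-score estimate, but that error is the same removable variance seen conditionally. It is not an additional bias, and the change-score standard error already covers it. Precision still matters here, because the primary comparison targets 0.12 m/s with 24 children per arm.

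**Working it through.** **Inputs from Power Calculations.** Two-sided 0.05; difference 0.12 m/s in mean change; 24 per arm, or 19 per arm after dropout; SD 0.167 m/s, read as the SD of change.

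**The plan's own figure.** With these inputs a two-sample t test has 68.3% power, not the stated 90%. With 0.127 m/s, the SD printed for fast gait speed, it has 89.3%. Which SD belongs to the primary outcome is a separate issue, so both are carried below.

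**Assumed inputs, not in the documents.** r is the correlation of baseline with the 8-week value within site and GMFCS level. k is the 8-week SD divided by the baseline SD.

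**Formulas.**
- Error df of the change model: total minus 6 (intercept 1, treatment 1, site 1, GMFCS 2, gender 1). That is 48 - 6 = 42, or 38 - 6 = 32. Adding baseline gives 41 or 31.
- Variance ratio, adjusted to change: k²(1 - r²) / (1 + k² - 2rk), which is (1 + r)/2 when k = 1.
- Cost of estimating the slope: multiply by 1 + 1/(df - 1), with df from the adjusted model. This is 1.025 at df 41 and 1.033 at df 31.
- Power from the noncentral t, with noncentrality 0.12 / √(2·SD²·ratio/n).

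**One case worked.** SD 0.167, n = 24, r = 0.5, k = 1. The standard error of the change contrast is 0.167 × √(2/24) = 0.0482, so the noncentrality is 2.489 and power is 0.682. The net ratio is 0.75 × 1.025 = 0.769. The noncentrality becomes 2.489/√0.769 = 2.84 and power 0.792, a gain of 11.0 points.

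**Power for 0.12 m/s, net of slope estimation, k = 1.**

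| n per arm | SD | Change only | r = 0.5 | 0.7 | 0.8 | 0.9 | 0.95 | Slope exactly 1 |
|---|---|---|---|---|---|---|---|---|
| 24 | 0.127 | 0.892 | 0.954 | 0.928 | 0.914 | 0.899 | 0.892 | 0.884 |
| 24 | 0.167 | 0.682 | 0.792 | 0.740 | 0.716 | 0.693 | 0.681 | 0.670 |
| 19 | 0.127 | 0.806 | 0.893 | 0.853 | 0.833 | 0.813 | 0.803 | 0.793 |
| 19 | 0.167 | 0.575 | 0.683 | 0.629 | 0.605 | 0.582 | 0.571 | 0.560 |

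The last column is the worst case: a loss of 0.8 and 1.1 points at 24 per arm, and of 1.4 and 1.5 at 19. Net break-even with equal variances is r of about 0.95 at 24 per arm and 0.93 at 19.

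**If the SD rises by 10% (k = 1.1), change in power, points.**

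| n per arm | SD | r = 0.5 | 0.7 | 0.8 | 0.9 |
|---|---|---|---|---|---|
| 24 | 0.127 | +4.5 | +1.6 | +0.2 | -0.8 |
| 24 | 0.167 | +7.5 | +2.4 | +0.3 | -1.1 |
| 19 | 0.127 | +6.0 | +1.8 | -0.1 | -1.3 |
| 19 | 0.167 | +7.1 | +2.0 | -0.1 | -1.4 |

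**What each r implies.** Because the SD of change is held fixed, r also sets the baseline SD within strata: SD/√(2(1 - r)) at k = 1. For r = 0.5, 0.8 and 0.9 this is 0.127, 0.20 and 0.28 m/s (SD 0.127), or 0.167, 0.26 and 0.37 m/s (SD 0.167).

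**Check that baseline imbalance and lost variance are one quantity.** With SD 0.127, n = 24 and k = 1, the change contrast has standard error 0.0367. A baseline gap of one standard error shifts the estimate by 0.50, 0.39 and 0.22 of that at r = 0.5, 0.7 and 0.9. Squared, these are 25%, 15% and 5%, which equal 1 - (1 + r)/2.

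**Simulation.** The full model was simulated with 20,000 replicates at SD 0.127, assuming 8 children per GMFCS level per site, 1:1 allocation and random gender.
- At 24 per arm the change model had power 0.881 to 0.885. With baseline it was 0.948, 0.919, 0.909 and 0.887 at r = 0.5, 0.7, 0.8 and 0.9 (k = 1).
- At 19 per arm, with random loss, the change model had 0.783 to 0.793. With baseline it was 0.876, 0.839, 0.821 and 0.795.
- Both estimators averaged 0.120 m/s, and type I error at r = 0.8 was 0.049 for both models.

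**The case against.** The strongest reply is that nothing here is an error. The change-score analysis is prespecified, unbiased and consistent with the sample-size section, and site and GMFCS level are already blocked and modelled. The choice is between two legitimate estimators. That stands, and it is why the point is rated low.

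The size also rests wholly on assumed r and k. The 11-point gain is one corner: r = 0.5, equal variances and the printed SD of 0.167, which does not reproduce the stated 90%. At 0.127 the top is about 6 points. That corner also needs baseline speeds within a stratum to vary no more than the 8-week changes do. Averaging three trials reduces measurement noise and leans towards higher r, where the gain is small, although varied response to training could still lower it. These limits stand.

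At 19 per arm a 10% rise in SD removes the gain at r = 0.8. The formula and the simulation also differ by 1 to 2 points there (0.806 against 0.783 to 0.793 for the change model), which is more than the gain at r = 0.9. Absolute power at that size should therefore be read loosely.

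None of this defeats the point. The loss is bounded at about 1 to 1.5 points, while the possible gain is several.

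**Conclusion.** The concern holds, as a low-severity improvement in precision. The primary model omits a baseline value that the trial collects. At 24 per arm, for r of 0.5 or more, including it would change power by about -1 to +11 points if the SD of change is 0.167 m/s, and by about -1 to +6 if it is 0.127 m/s. At 19 per arm the worst loss is about 1.5 points. The effect is positive in most of the assumed cases, but that describes the grid and not this trial: the documents supply no slope, correlation or baseline SD. Adjustment would not restore 90% power at SD 0.167, where even r = 0.5 reaches only 79%.

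**What to change.** In the Data Analysis Plan, prespecify the baseline value of the same outcome as a continuous covariate in the baseline-to-8-week general linear model for the primary outcome, alongside treatment, site, GMFCS level and gender. Do the same in that model for the secondary outcomes; the gain there is not quantified here. The response may stay as change, because once baseline is in the model the treatment estimate is identical to the one with the 8-week value as response.

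Do not add baseline as a covariate to the four-time-point mixed model, where it is already one of the responses. The two models' 8-week estimates may then differ, so add a clause confirming that the general linear model gives the primary 8-week effect. The plan largely says this already, and the covariate change does not depend on it.

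The cost is one sentence and a clause, one error degree of freedom (42 to 41, or 32 to 31 at 19 per arm), and variance inflation of about 2.5% at 24 per arm or 3.3% at 19. No new data are needed. The change should be made before unblinding, since a covariate added later would look selective.

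### The retention mixed model names a random subject effect and no residual covariance; if within-child correlation falls with time, a test of baseline-to-6-month change would have type I error of about 7 to 14%

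*Combined protocol and SAP*

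**What the plan says.** Under Testing / Assessment Protocols, outcomes are measured before and after the 8-week intervention, then "at 2 months post for short-term retention; and 6 months post for long-term retention". Counted from baseline, that is about 0, 2, 4 and 8 months, and "a 2-week window will be allowed for all assessment timepoints".

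The Data Analysis Plan describes two models:

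- For the main comparison: "The primary analysis will compare differences in changes from baseline to 8 weeks post in mean response", using a general linear model with site and GMFCS level as blocking factors.
- For retention: "To gain insight into both short and long-term retention of treatment effects", the plan states that "response profiles over the 4 time points will be compared using a linear mixed effects model". This model has the same blocking factors, "treatment group and time as fixed effects factors, and subjects as a random factor".

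The software is given as the GLM and MIXED procedures of SAS. For the retention model the plan writes no residual covariance structure, no treatment-by-time term, no contrast at 2 or 6 months, and no degrees-of-freedom method. The same models are to be used for the primary and secondary variables of Aims 1 and 2, and similar ones for Aim 3.

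**The concern.** A random subject intercept with independent residuals is a compound-symmetry model. It takes baseline and the 6-month visit, about 8 months apart, to be as strongly correlated as baseline and the post-treatment visit, about 2 months apart. It then uses one pooled within-child variance for every change contrast. If correlation falls as the gap widens, that pooled variance is too small for the longest gap and too large for the shortest.

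Retention is part of Aim 1, and this model is the only analysis described for it. If the retention result is reported as a group difference in change from baseline to 6 months, parallel to the primary estimand, its confidence interval could be too narrow and its p-value too small.

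**Working it through.** The documents give no power or precision figure for the retention model, so there is nothing of the plan's own to reproduce here.

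**Inputs from the documents.** 24 children per group (Power Calculations); "Type I error rate will be set at 0.05" (Data Analysis Plan); "a 0.050 two-sided significance level" (Power Calculations); visits at about 0, 2, 4 and 8 months (Testing / Assessment Protocols).

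**Inputs assumed.** Within-child correlations and visit-specific SDs are not given, so a range is used. Data are taken as complete, and the blocking factors are left out.

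**Method.** For complete balanced data, a random-intercept model with independent residuals is the split-plot analysis of variance. Its within-child error has 46 × 3 = 138 degrees of freedom. For the group difference in change between visits i and j:

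- ratio = true variance / model variance = Var(Yi − Yj) / [2 × (mean variance − mean covariance)]
- actual type I error = 2 × P(t138 > 1.977 / √ratio), where 1.977 is the two-sided 5% critical value.

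**Worked case: pure decay of 0.90 per 2 months, equal SDs.**

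1. The six pairwise correlations are 0.900, 0.810 and 0.656 (baseline with post, 2 months post, 6 months post), 0.900 and 0.729 (post with the two later visits), and 0.810 (2 with 6 months post). They sum to 4.805, so the mean is 0.801.
2. For baseline to 6 months, ratio = (1 − 0.656) / (1 − 0.801) = 0.344 / 0.199 = 1.73.
3. 1.977 / √1.73 = 1.50, which gives a type I error of 13.5%.

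**Range.** The last column is the overall group-by-time test, from 20,000 simulated trials per scenario.

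| Assumed pattern | Ratio, baseline to 6 months | Type I error, that contrast | Type I error, overall profile test |
|---|---|---|---|
| Constant correlation, 0.5 or 0.8 | 1.00 | 5.0% | 5.1% |
| Pure decay, 0.95 per 2 months | 1.79 | 14.1% | 6.9% |
| Pure decay, 0.90 | 1.73 | 13.5% | 6.9% |
| Pure decay, 0.80 | 1.61 | 12.2% | 6.6% |
| Pure decay, 0.70 | 1.50 | 10.9% | 6.3% |
| Decay 0.80 to 0.95, with 10 to 30% of variance as independent visit error | 1.15 to 1.47 | 6.8 to 10.5% | not run |
| Stable child component plus decay: a + b·exp(−gap/4), (a, b) = (0.6, 0.3), (0.7, 0.2), (0.5, 0.3) | 1.19 to 1.26 | 7.3 to 8.1% | 5.2 to 5.3% |
| Baseline with 6 months 0.9, all other pairs 0.8 | 0.55 | 0.8% | 5.7% |
| Constant correlation 0.8, SDs 1, 1.2, 1.2, 1 | 0.79 | 2.7% | 5.2% |

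**Other contrasts from the same model.**

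- Baseline to 2 months post is close to nominal: 4.3 to 5.2% across the decay patterns.
- Baseline to post is conservative: 0.5 to 0.8% under pure decay of 0.80 to 0.95.
- The group difference at the 6-month visit itself, with equal SDs, stays at 5%.

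**Simulation check.** In the simulated trials the random-intercept model gave 11.3 to 14.5% for baseline-to-6-month change under pure decay, slightly above the closed form. An unstructured covariance, which for complete data amounts to a t test on the change with 46 degrees of freedom, gave 4.8 to 5.1% in every pattern simulated. That includes the two patterns in which the random intercept is conservative.

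**The case against.** A reader might infer that the plan forces equal correlation and therefore makes the 6-month retention test anti-conservative. The documents do not support that.

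- The plan lists effects and names the MIXED procedure, which can combine a random subject with a structured residual. Independent residuals are the literal reading of the text, not a stated commitment.
- Unequal spacing alone inflates nothing. The true covariance has to depart from compound symmetry in a particular direction, and the documents give no correlations or visit-specific SDs from which to judge this. The last two rows of the table go the other way.
- The 12 to 14% figures need pure decay with no visit-level error. That is unlikely for gait speed averaged over three walk trials, and modest visit error brings the figure down to about 7 to 10%.
- The plan does not define the contrast that is inflated. It compares profiles over four visits, and that test is only mildly affected.
- The retention analysis is supportive, in a study whose Purpose section calls it a pilot.

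All of this stands, and it is why the size is stated conditionally. It does not remove the point. Change from baseline to 6 months is the natural reading of a retention effect, decay over time is a plausible pattern in 10- to 17-year-olds, and the alternative covariance holds its level whichever pattern is true.

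**Conclusion.** The concern holds conditionally. The retention model leaves its covariance unstated. Taken literally, it assumes equal correlation over gaps of about 2 to 8 months. If correlation declines with time, the type I error for baseline-to-6-month change is about 7 to 14%: about 7 to 10% in the more realistic patterns, and 12 to 14% only under pure decay of 0.80 to 0.95 per 2 months. If correlation is constant it is 5%, and under some patterns it is below 5%. The overall profile test stays at about 5 to 7%.

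These figures rest on assumed correlations, complete data, 24 children per group and independent residuals. The conclusion on the primary 8-week comparison is untouched, because that comparison does not use the mixed model. The change should be made before the data are analysed, but it does not threaten the trial's main result.

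**What to change.** In the Data Analysis Plan, for the retention model:

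1. Replace the random intercept alone with an unstructured covariance over the four visits (in PROC MIXED, REPEATED time / SUBJECT=id TYPE=UN) and Kenward-Roger degrees of freedom.
2. Name a fallback in case it does not converge, for example heterogeneous Toeplitz, or spatial power on actual months since baseline.
3. Include the treatment-by-time term.
4. Define the retention tests as the group differences in change from baseline to 2 months post and from baseline to 6 months post.

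The cost is a few lines of text and 10 covariance parameters instead of 2, which 48 children can support. If correlation is in fact constant, a little precision is lost: with complete data the critical value rises from 1.977 (138 degrees of freedom) to 2.013 (46), so intervals are about 2% wider (2.013 / 1.977 = 1.018).
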